#### 9.6 Ib Treatment Period and Post-Treatment Assessments

- 1115 1) Subjects will receive MRG003 at MTD/RP2D via intravenous infusion for 8 cycles; 8 cycles will take more than 24 weeks for a total of 15 visits.
- Refer to Section 9.2 for the operations during the screening period and Section 9.3 for the operations during the first dosing.
- 1119 3) The dosing cycle was performed according to 6.
- 1120 4) Blood samples will be collected during the dosing period to determine PK parameters as specified in Table 7-2.
- Blood will be drawn to measure the subject's ADA antibody concentration at specified visits (see Table 6 of the visit schedule) to assess immunogenicity of the study drug.

- Subjects were assessed for antitumor efficacy every 6 weeks. Subjects with response of CR and PR should be assessed for response confirmation at subsequent Week 6. Efficacy assessment methods are described in Section 6.5. In addition to ORR indicators for anti-tumor efficacy, PFS, OS and DOR indicators for anti-tumor efficacy will also be evaluated.
- At the end of the last dosing, the study site should recall the subjects to the study site about 21 days later for a safety visit to understand the resolution of ongoing adverse events or abnormal changes in laboratory tests, and to evaluate the new adverse events, serious adverse events, new drugs or changes in current medication that have occurred since the last assessment.
- Vital sign parameters (pulse, blood pressure, body temperature), ECG, physical examination, including performance status score, height and weight, hematology, coagulation, blood biochemistry and urinalysis should be performed during the visits specified in Table 6. In addition, attention should be paid to whether additional examinations are required due to clinical indications at each visit during treatment, such as vital signs, ECG, neurological examination, routine blood examination, coagulation function test, blood biochemistry, urinalysis, and serum pregnancy test.
- 1141 9) Record AEs/SAEs and concomitant medications of subjects.
- 1142 10) Subject survival was recorded.

1144

1145

1146 1147

1148 1149

1150

# 9.7 Efficacy and Survival Follow-up

For subjects without disease progression after the end of 21-day treatment visit, antitumor efficacy assessment and survival follow-up should be performed every 6 weeks until disease progression or other anti-tumor treatment. After confirmation of disease progression or receipt of other antineoplastic therapy, patients were followed for survival every 12 weeks until death or study termination. See the data management plan of this study for the cut-off point of data collection in the case report form.

#### 9.8 Early termination of treatment

- 1151 Treatment of a subject may be discontinued early in the following circumstances:
- In case of uncontrolled adverse events, the investigator decides to stop treatment;
- The subject experienced disease progression;
- Subject died;
- Withdrawal of informed consent by the subject;
- Subject lost to follow-up.

In any case of premature treatment discontinuation, the investigator should make every effort to inquire about the reason for premature treatment discontinuation and record the discontinuation on the subject's eCRF form. When a subject prematurely discontinues treatment due to an AE/SAE, the investigator should follow the subject until the condition is cured or stable, and continue to complete imaging assessments and survival follow-up.

	10 TEST OPERATION GUIDELINE
	10.1 General operation
	Physical examination and baseline indicators:
	Standard demographic and baseline characteristics (including age, gender, race, height and weight, etc.), medical history, cancer diagnosis and prior anticancer therapy will be collected at baseline.
	• Imaging examination:
	CT, MRI: CT is currently the best and reproducible test for assessing anti-tumor efficacy. The lesion measurements defined in this study according to RECIST v1.1 were based on the assumption that the CT scan slice thickness did not exceed 5 mm. When CT scans have slice thickness greater than 5 mm, the minimum size for a measurable lesion (diameter) should be twice the slice thickness. MRI may also be used in certain situations (e.g. for body scans). For each identified and reported lesion, the same measurement technique and assessment method should be used at baseline and at follow-up. Further details on the use of CT and MRI examinations to assess objective tumour response are provided in Appendix II.
	10.2 Laboratory assessments
	10.2.1 Clinical Laboratory Assessments
1	10.2.1.1 Blood routine examination The subject's examination includes: red blood cell, white blood cell (neutrophil, eosinophil, basophil, lymphocyte, monocyte), hemoglobin, platelet and other related tests (white blood cell differential and absolute count collected and recorded).
	10.2.1.2 Coagulation test
	Coagulation test for subjects includes: prothrombin time (PT), activated partial thromboplastin time (APTT), fibrinogen, international normalized ratio (INR) and other related tests.
	10.2.1.3 Blood biochemistry
	The subject's serum biochemical examination (SBP) includes aspartate

The subject's serum biochemical examination (SBP) includes aspartate aminotransferase (AST), alanine aminotransferase (ALT), alkaline phosphatase, amylase, lipase, lactate dehydrogenase, γ-glutamyltransferase direct bilirubin and total bilirubin, total protein, blood glucose, potassium, sodium, calcium, creatinine, blood urea nitrogen (BUN) and other related tests.

If the serum creatinine concentration is  $> 1.5 \times ULN$ , creatinine clearance will be calculated (calculated according to age using the following formula).

1197 Cockroft-Gault calculation formula (female): 1198 Endogenous creatinine clearance rate (mL/min) =  $[(140\text{-age}) \times \text{body weight * (kg)}]$ 1199  $\times 0.85$ ]/[72 × serum creatinine (mg/dl)] 1200 OR  $[(140\text{-age}) \times \text{weight * (kg}) \times 0.85]/[0.818 \times \text{serum creatinine (umol/L)}]$ 1201 Cockroft-Gault calculation formula (male): Endogenous creatinine clearance rate (mL/min) =  $[(140\text{-age}) \times \text{body weight *}]$ 1202 1203 (kg)]/[72 × serum creatinine (mg/dl)] 1204 OR  $[(140\text{-age}) \times \text{weight * (kg)}]/[0.818 \times \text{serum creatinine (umol/L)}]$ 1205 \* Body weight: Body weight on D1 was used to calculate all creatinine clearance in the 1206 first dosing cycle 1207 10.2.1.4 Carcinoembryonic antigen test 1208 Carcinoembryonic antigen testing was performed in all colorectal cancer patients 1209 during odd dosing cycles (i.e., Cycles 1, 3, 5, and 7). 1210 10.2.1.5 Urine test 1211 Urinalysis: urine color, transparency, pH, specific gravity, white blood cells, nitrite, 1212 occult blood, qualitative protein, qualitative and microscopic examination of urine glucose 1213 (if white blood cells, nitrite, total protein, or occult blood are positive, microscopic 1214 examination will be performed). 1215 10.2.1.6 Serum pregnancy test 1216 Serum human chorionic gonadotropin (HCG) levels were measured by conventional laboratory methods in women for the diagnosis of early pregnancy. Pregnant women 1217 1218 generally have a positive serum pregnancy test after 35 days of menopause. 1219 10.2.1.7 Infectious Disease Testing 1220 To detect HIV, HBsAg and anti-HCV antibody in the blood of subjects. **10.2.2 Special Experimental Assessments** 1221 1222 10.2.2.1 Genetic testing 1223 Handling of new tissue biopsy specimens or archived specimens is described in the 1224 Laboratory Manual. Subject pathology specimens should be sent to a third party laboratory 1225 at pre-screening and/or screening as requested by the sponsor in an appropriate manner. 1226 Third-party laboratories are responsible for detecting EGFR protein expression and EGFR 1227 targeted sequencing, KRAS, NRAS and BRAF gene hotspot mutation detection.

## **10.2.2.2 Determination of metabolic parameters of study drug**

- Blood samples (8) were collected according to the visit schedule (Table 6 and Table 7), and the serum concentrations of three components of MRG003: conjugated antibody (MRG003), total antibody (conjugated antibody + naked antibody), and free small molecule toxin MMAE were determined by a validated method at a third-party bioanalytical laboratory.
- In the first dosing cycle of Phase Ia and Phase Ib, PK parameters of MRG003 in all subjects will be analyzed by non-compartmental method, but not limited to  $C_{max}$ ,  $T_{max}$ ,  $t_{1/2}$ , MRT,  $V_d$ , CL, AUC0-t and AUC0-inf.

# 10.2.2.3 Study Drug Immunogenicity Assay

Immunogenicity refers to the drug attribute that protein drugs are injected into patients to cause adverse immune response. Immunogenicity can interfere with the kinetic parameters of protein drugs and the effectiveness of drugs. Anti-therapeutic drug antibodies (ADAs) have the potential to trigger allergic reactions, anaphylactic shock, and inflammatory reactions in patients.

In this study, blood was collected from subjects (see Table 6 and Table 7 for details) before the start of each dosing cycle and at the end of the dosing cycle (before the next dosing) to extract serum samples (8). Serum samples were temporarily stored at the laboratory of the research hospital below  $-60\,^{\circ}$  C. Subject serum samples will be shipped to a third party bioanalytical laboratory by appropriate methods on schedule at the request of the Sponsor. Immunogenicity and corresponding ADA assays for MRG003 included a screening assay, a confirmatory assay, and an assay.

#### 10.3 Permitted concomitant medications and treatments

Due to the unique nature of oncology patients, subjects were allowed to receive adequate supportive care during the study as medically necessary and documented in the eCRF.

- 1) During the trial treatment, when the study drug causes acute toxic reactions, such as febrile neutropenia, the investigators should decide to give the subjects biological response modifiers (BRMs), such as G-CSF or GM-CSF, in combination with other concomitant symptoms and risk factors of clinical patients. The specific protocol can follow the clinical medication routine of each hospital; however, the use of biological response modifiers for patients to meet the trial inclusion criteria is not allowed, and the use of prophylactic biological response modifiers during the first dosing cycle is not allowed.
- 2) Prophylactic anti-allergic treatment, preventive antiemetic treatment;
- 3) Therapeutic use of antibiotics, e.g., in case of febrile neutropenia or infection;
- 4) In case of diarrhea, antidiarrheal treatment should be performed according to the routine of the hospital;

- Palliative radiotherapy for analgesic purposes may be given (if bone metastases occur) to control pain. The irradiated area should be as small as possible. No target tumor lesion should be included in the irradiated area, otherwise the patient will be excluded from the trial, and the patient will not participate in the evaluation of tumor response. Radiation area can not be used as the parameter for response evaluation;
  - 6) Other symptomatic treatment for drug toxicity may be given at the discretion of the investigator based on the specific condition of the subject and should be recorded in detail in the eCRF.

#### 10.4 Prohibited concomitant medications and treatments

- 1) Patients are not allowed to receive other forms of anti-tumor therapy, including chemotherapy, immunotherapy, endocrine anti-tumor therapy, surgical therapy or other investigational drugs during the study. Whether the concomitant drug has anti-tumor effect shall be subject to the content in the package insert. Any disease progression requiring other anti-tumor treatment will lead to premature discontinuation of the study treatment;
- 2) Administration of radiotherapy (except palliative radiotherapy for pain relief purposes) is not allowed.

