According to the literature (Lin-2013), the biodistribution of ADC is similar to the

Experimental results on the cross-reactivity of Cetuximab with mouse, rat, cynomolgus monkey and human tissues showed that Cetuximab only bound to the epithelial cells of cornea, placenta, prostate, liver, lung bronchus, esophagus, mammary gland and salivary gland of human and monkey eyes, as well as the linear and squamous epithelial cells of skin, but did not bind to the tissues of mouse and rat (FDA Erbitux ® Pharmacology Review). This was generally consistent with the results of tissue cross-reactivity test of MRG003 in normal subjects and cynomolgus monkeys.

Metabolism and Excretion of MMAE In the marketed Adcetris ® studies, Adcetris ® was shown to be highly stable, with only a very small fraction of extracellular MMAE released from the ADC and metabolized, producing free drug as well as concentrations insufficient to cause cytotoxicity.

The results of in vitro [H] -MMAE metabolic phenotyping study showed that [H] -MMAE was converted into eight radioactive substances by human liver microsomal NADPH. Metabolites are produced primarily by O-demethylation, N-demethylation, and dehydrogenation and are mediated by CYP3A4, with other CYP450 enzymes likely involved in the formation of only a small fraction.

In the study of in vitro determination of the metabolic characteristics of [H] -MMAE in liver microsomes from different animal species and humans, rat, monkey, and human hepatocytes were incubated with 10 µM [H] -MMAE for 0, 60, 120, and 240 min, respectively, and a total of 12 compounds were found, and the migration of molecular weight was mainly through hydroxylation, demethylation, dehydrogenation, or hydrolysis. Among them, all 12 compounds were detected in monkey hepatocytes, and 9 compounds with slight differences were detected in rats and humans.

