Inhibition of human hepatic cytochrome P450 enzymes by MMAE experiments primarily determined the inhibitory effect of MMAE on major CYP enzymes (CYPIa2, CYP2B6, CYP2C8, CYP2C9, aCYP2C19, CYP2D6, CYP3A4/5). In the experiment, human liver microsomes were incubated with different concentrations of MMAE (0.1-100  $\mu$ M). The results showed that MMAE could directly inhibit CYP3A4/5 through midazolam 1 'hydroxylation at IC50 of 10  $\mu$ M, and testosterone 6 $\beta$ -hydroxylation had little or no direct inhibition on CYPIa2, CYP2B6, CYP2C8, CYP2C9, CYP2C19, CYP2D6 or CYP3A4/5 at IC50 > 100  $\mu$ M. MMAE inhibited CYP3A4/5 in a time-dependent manner.

The results of the excretion test of Adcetris® in rats showed that after intravenous administration of 3 mg/kg Adcetris ® (cAC10-vc-3H-MMAE) or 0.056 mg/kg 3H-MMAE, urine and feces were collected at intervals of 24 h (up to 672 h) from 0 to 12 h and 12 to 24 h. The concentrations of radioactivity in blood, plasma, urine, feces, and carcasses were determined by LS, the types of emitted substances in urine and feces were determined by HPLC/UV, and the main metabolites were detected by LC-MS/MS. The results showed that the main elimination pathway of cAC10-vc-3H-MMAE and 3H-MMAE in rats was through feces, and part of it was excreted through urine. Approximately 89% (males) or 97% (females) of the cAC10-vc-3H-MMAE radioactivity was detected in feces and

approximately 14% (males) or 7% (females) in urine. Of the 3H-MMAE, approximately 97% (males) or 102% (females) of the radioactivity was detected in feces, and approximately 15% (males) or 9% (females) of the radioactivity was detected in urine. In summary, the metabolic pattern and metabolites of MMAE were similar in rat, monkey, and human liver microsomes, and MMAE inhibited CYP3A4/5 but not other CYP isoforms. MMAE did not induce CYP450 enzymes in human hepatocytes. Metabolism of MMAE occurs primarily through oxidation by CYP3A4/5. MMAE is excreted primarily in the feces and partially in the urine, primarily as unchanged MMAE (Adcetris ® FDA Pharmacology Review). 

In addition, in a clinical human MMAE metabolism study, it was found that approximately 72% of MMAE recovered in feces after Adcetris® was intravenously infused at 1.8 mg/kg for one week, which was consistent with the results of preclinical studies. (Adcetris® Labeling)

448	5 TRIAL OBJECTIVE
449	5.1 Primary Trial Objectives

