#### **6.3.2** Selection of maximum dose

581

582

583

584

585

586587

588

589

590

591

592

593 594

595

596

597598

599

600

601 602

603

604

605

606

607

608

609

610

611

612 613

614

615

The maximum dose that may be achieved during the dose escalation phase is 3.0 mg/kg. According to several clinical trials of vcMMAE-based ADC drugs for different targets in Europe and the United States, DLT is usually caused by the toxicity of MMAE, and MTD is generally occurred at the dose of 1.8 – 2.4 mg/kg.

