#### **6.3.3 Dose Escalation Scheme**

MRG003 will be assessed for dose-limiting toxicity during the first treatment cycle of Phase Ia. Intravenous drip of a certain dose of MRG003 was given to the patient for recuperation for 3 weeks, which was considered as 1 treatment cycle. In the drug tolerance study, the modified accelerated titration dose escalation method was followed for the early two dose groups (0.1, 0.3 mg/kg), and the standard 3 + 3 (modified Fibonacci method) dose escalation method was followed for the subsequent dose groups (0.6, 1.0, 1.5, 2.0, 2.5, 3.0 mg/kg). The escalated doses and the number of subjects are presented in Table 2. In the 0.1 mg/kg and 0.3 mg/kg dose periods, only 1 subject was required. If a subject experiences an adverse reaction at 0.1 mg/kg and meets the DLT criteria, the tolerance test protocol will be converted to the 3 + 3 method (i.e., add another 2 subjects in the 0.1 mg/kg dose group); if the adverse reaction of a subject does not meet the DLT criteria, the tolerance test can enter the next dose group. Doses of 0.6 mg/kg and higher were escalated by the 3 + 3 method. In any dose group, if none of the 3 subjects experienced DLT at the end of treatment cycle, the tolerance test could enter the next higher dose group; if 1 of the 3 subjects experienced DLT at the end of treatment cycle, another 3 subjects were included in this dose group. If none of the additional 3 subjects experienced DLT, the tolerance test could enter the next dose group. If 2 or more of 3 or 6 subjects in a dose group experienced DLT, dose escalation was stopped and the previous low dose group was the maximum tolerated dose (MTD). To find a more accurate MTD, an intermediate dose group may be added to the preset dose based on available safety and PK data. Dose escalation plan see Table 2. If the MTD is not observed in the above dose groups, dose escalation will continue in a 3 + 3 manner by escalating no more than 20% of the previous dose level until the MTD is reached. In the 3 + 3 escalation method, each subject received only one corresponding dose. The next escalating dose was not entered until the end of each dose observation. Trials with more than two dose groups could not be performed simultaneously. See Table 3 for the judgment principles of MTD or RP2D.

Table 2: Dose escalation scheme and number of subjects

Dose Group	1	2	3	4	5	6	7	8	9 above
Escalation		200%	100%	67%	50%	33%	25%	20%	< 20%

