#### 6.3.4 Dose-limiting toxicity, maximum tolerated dose and recommended phase II dose

#### 6.3.4.1 Judgment criteria for dose limiting toxicity (DLT)

A DLT was defined as an AE (except allergic reaction) or abnormal laboratory value not related to disease progression, or concomitant disease, or concomitant medication, and met any of the following criteria in the DLT table (Table 4). Adverse events will be assessed according to CTCAE v4.03. Any subject who fails to complete the 21-day observation period for reasons other than DLT will be considered as not evaluable for DLT, and another subject in the same dose group should be added.

Table 4: Judgment criteria for DLT according to CTCAE 4.03 classification

Toxicity	Any of the following criteria
Blood	Grade 4 neutropenia lasting > 7 consecutive days
	Grade 3 thrombocytopenia lasting > 7 consecutive days
	Grade 4 thrombocytopenia
	Grade 3 febrile neutropenia (granulocytes < 1.0 × 109/L, body temperature ≥ 38.5°C) requiring antibiotics
Kidney	Serum creatinine greater than 3 times the upper limit of normal for > 7 consecutive days
	≥ Grade 3: Blood creatinine increased
Liver	Total bilirubin greater than 3 times the upper limit of normal for > 7 consecutive days
	≥ Grade 3 total bilirubin elevation
	Grade 3 AST or ALT elevation lasting > 7 consecutive days
	Grade 4 elevated aspartate aminotransferase (AST) or alanine aminotransferase (ALT)
Pancreas	Symptomatic amylase or lipase abnormalities ≥ CTCAE Grade 3
	Asymptomatic ≥ CTCAE Grade 3 amylase or lipase abnormality lasting longer than 7 days
Cardiovascular system	≥ Grade 3
Eye	≥ Grade 3
Skin	Grade 3 or 4 skin toxicities that remain uncontrolled despite symptomatic treatment
Nervous system	≥ Grade 3: Neurologic toxicity
Other Adverse Events	≥ Grade 3: Uncontrolled vomiting and nausea despite the use of antiemetic doses
	≥ Grade 3: Uncontrolled diarrhea despite the subject's use of antidiarrheal medication
	Treatment delay of > 14 days due to unresolved toxicity that does not resolve to Grade 1 or baseline
	Other ≥ Grade 3 AE

Any other unacceptable toxicity as determined jointly by the investigator and the sponsor's medical monitor

Note: 3 kinds of adverse reactions are not regarded as criteria for DLT judgment:  $\geq$  Grade 3 anemia (unless there is indirect relationship with MRG003);  $\geq$  Grade 3 lymphocytopenia (unless there is clinical significance);  $\geq$  Grade 3 hypercholesterolemia or hypertriglyceridemia.

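### No limit on strong CYP3A4 inhibitors or inducers in Cycle 1, although the protocol names CYP3A4/5 as the main metabolic route of MMAE and MMAE as the usual cause of DLTs

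*Protocol*

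**What the plan says.** **Metabolism and toxicity.** Section 4.2.2.2 says "Metabolism of MMAE occurs primarily through oxidation by CYP3A4/5". It adds that the metabolites formed in human liver microsomes "are mediated by CYP3A4, with other CYP450 enzymes likely involved in the formation of only a small fraction". On vcMMAE conjugates in general, section 6.3.2 says "DLT is usually caused by the toxicity of MMAE".

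**Statements that limit the point.** Section 4.2.2.2 also says "MMAE is excreted primarily in the feces and partially in the urine, primarily as unchanged MMAE". For the marketed vcMMAE conjugate it reports little extracellular release and "concentrations insufficient to cause cytotoxicity".

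**Co-medication.** The first item of section 10.4 reads "Patients are not allowed to receive other forms of anti-tumor therapy, including chemotherapy, immunotherapy, endocrine anti-tumor therapy, surgical therapy or other investigational drugs"; the second bars radiotherapy other than for pain. Section 10.3 permits antibiotics, antiemetics, anti-allergic and antidiarrhoeal drugs and other symptomatic treatment, with no condition about CYP3A4. Its one limit specific to Cycle 1 is a ban on prophylactic biological response modifiers.

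**DLT and escalation.** Section 6.3.4.1 requires a DLT to be "not related to disease progression, or concomitant disease, or concomitant medication". Section 6.3.3 says "If 2 or more of 3 or 6 subjects in a dose group experienced DLT, dose escalation was stopped". DLTs are assessed over Days 1 to 21. Section 10.2.2.2 has Cycle 1 PK parameters analysed in all subjects, and free MMAE is one of the three analytes.

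**The concern.** The protocol names the component that usually causes DLTs in this class and the enzyme that mainly metabolises it, but the co-medication rules take no account of the link. A subject may enter on, or start during Cycle 1, a drug that strongly inhibits or induces that enzyme. If this changed MMAE exposure, a DLT could appear or fail to appear for a reason other than the assigned dose. Free-MMAE parameters for that subject would reflect the co-medication as well as the dose.

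At stake is the MTD or RP2D. It is set from very small cohorts, PK is one of the stated inputs to the RP2D (section 6.3.4.2), and the selected dose is carried into Phase Ib. Co-medication rules and the DLT definition belong in the protocol, so this is not a detail left to a statistical analysis plan.

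**Working it through.** The protocol gives no figure to reproduce. The check has three steps.

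**1. Is such a drug restricted anywhere?**

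- Sections 7.3 and 7.4: no criterion names CYP3A4 drugs. The nearest, exclusion 13, concerns concomitant disease.
- Section 10.3: permits the classes listed above without a CYP3A4 condition.
- Section 10.4: anti-tumour treatment, investigational drugs and radiotherapy only.
- Section 7.5.1: the investigator may withdraw a subject using drugs that affect the safety judgment. This is discretionary and follows exposure.
- Section 7.7: refers to drugs outside a specified range, but no range is given for CYP3A4 drugs. Excluded cases enter the safety analysis at discretion.
- Table 6: concomitant medication is recorded continuously. That detects use but does not prevent it.

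No clause limits these drugs before or during Days 1 to 21 of Cycle 1.

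**2. What can one DLT change?** This uses section 6.3.3, Table 3 and the MTD definition in section 6.3.4.2, with no rate assumed. One subject is 1/3 = 33% of a cohort of three, or 1/6 = 17% of six.

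| Counts compared | Decision at the lower count | Decision at the higher count |
|---|---|---|
| 0/3 and 1/3 | escalate | add 3 subjects |
| 1/3 and 2/3 | add 3 subjects | stop |
| 1/6 and 2/6, during escalation | escalate | stop |
| 1/6 and 2/6, lower dose group expanded after a stop above it | MTD confirmed | MTD definition not met |
| 2/3 and 3/3 | stop | stop |

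Reading left to right is one DLT more; right to left is one fewer. Six subjects are reached in two ways: from 1/3 during escalation, or from 0/3 when Table 3 expands the previous dose group after the next dose is stopped. At the single-subject 0.1 mg/kg level, one DLT converts the scheme to 3+3 by adding two subjects.

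**3. Illustration with assumed rates.** The document gives no DLT rate and no interaction size, so every probability here is an assumption. The chance of passing a dose level is

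P(pass) = P(0 DLTs in first 3) + P(1 DLT in first 3) × P(0 DLTs in second 3).

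- All subjects at 0.20: 0.512 + 0.384 × 0.512 = 0.709.
- One subject per cohort of three raised to 0.40: 0.384 + 0.448 × 0.384 = 0.556. Raised to 0.30 or 0.50 instead, the result is 0.634 or 0.474.
- One subject per cohort lowered to 0.10: 0.576 + 0.352 × 0.576 = 0.779. Lowered to 0.05, it is 0.812.
- All subjects at 0.30: 0.343 + 0.441 × 0.343 = 0.494. One per cohort at 0.50: 0.245 + 0.455 × 0.245 = 0.356. One per cohort at 0.05: 0.4655 + 0.4235 × 0.4655 = 0.663.

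These figures show how sensitive the rule is if a subject's risk is altered. They are not evidence that it would be.

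**The case against.** **No interaction is shown.** Nothing in the document reports an inhibitor or inducer changing MMAE exposure, or ties systemic free MMAE to DLTs. Excretion mainly as unchanged drug and the low free-drug levels of the marketed conjugate argue against a large effect. This stands, and it limits the point to a possibility of unknown size and direction. A reader might infer that the MTD will be biased, or biased downward; the text supports neither.

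**Much permitted co-medication follows toxicity.** Grade 3 febrile neutropenia requiring antibiotics is already a DLT in Table 4, so the antibiotic given for it cannot have caused that DLT. This is correct for such cases. It does not cover drugs already taken at entry, antibiotics for other infections, or prophylactic treatment.

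**Section 6.3.4.1 can be read sensibly.** A reader might infer that it drops interaction events from the DLT count. The text does not support that: toxicity caused by MMAE naturally reads as study-drug toxicity, even if another drug raised exposure. Section 11.2.2 asks whether concomitant medication explains an event, and an uncertain answer is compatible with a possible relationship. Table 4 also allows a joint decision that any other unacceptable toxicity is a DLT. What remains is that no sentence says how an interaction event is counted, which is a secondary clarification.

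**Any 3+3 design is sensitive to one DLT.** This is true. The decision table shows only why an avoidable source is worth removing.

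**There are safeguards.** SMC review, intermediate doses, about three extra subjects at the lower dose, dense Cycle 1 sampling and wider RP2D inputs all help. They act after exposure and do not keep the drugs out of the DLT window.

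**Conclusion.** The point holds as a cheap improvement. Following the protocol as written permits strong CYP3A4 inhibitors and inducers throughout the Cycle 1 DLT and PK window, although its own background gives the reason to restrict them. The consequence is possible, avoidable distortion of DLT counts and of free-MMAE parameters. The document does not link the other two analytes, total and conjugated antibody, to CYP3A4.

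The size and frequency cannot be derived. The conclusion assumes that at least one subject takes such a drug and that it changes MMAE exposure enough to matter; otherwise there is no effect. If a DLT count shifts by one, the decision changes at the boundaries tabulated above. A reader might also infer that section 10.4 is wrong or contradicts section 4.2.2.2. It does neither: it omits a precaution that the background would justify.

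**What to change.** In section 10.4, prohibit strong CYP3A4 inhibitors and inducers, with a washout before the first dose, through Day 21 of Cycle 1. Where use is unavoidable, report it to the SMC when it reviews that cohort. Section 10.3 already sets a Cycle 1 limit for prophylactic biological response modifiers, so a rule of this kind fits the design.

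As a secondary clarification in section 6.3.4.1, state that toxicity attributable to MRG003 or MMAE counts as a DLT even if a co-medication may have raised exposure.

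The cost is one list item and one clause, with no new data collection because concomitant medication is already recorded. Some subjects will need an alternative co-medication, and the MTD may be slightly conservative.
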